7.3.8 Lumbar Puncture and CSF Assessment

An assessment of the cerebrospinal fluid (CSF) will be performed at screening if there is a concern of CNS lymphoma involvement or during treatment period if subject has a seizure. Cerebrospinal fluid, cell count, glucose, and protein will be measured at the

local laboratory as part of the examination to ensure that no infiltration of the CSF by DLBCL is present. Lumbar puncture performed up to 49 days prior to enrollment may be used in place of protocol-required assessments. Additional investigations of the CSF should be performed as clinically appropriate. Cerebrospinal fluid analysis will occur each time lumbar puncture is performed.

7.3.9 Brain MRI or CT

A brain MRI is required for all subjects at screening; if MRI is contraindicated (eg, pacemaker, implant, et al) a CT can be performed. Available results of brain contrast-enhanced MRI (or CT **if MRI contraindicated**) performed up to 8 weeks prior to first day of study treatment are acceptable. In case of neurological adverse event of grade 3 or higher, a brain MRI or CT should be performed.

7.3.10 Bone Marrow Biopsy

A bone marrow biopsy will be performed at screening. Bone marrow biopsy is only required to be repeated with response assessments in case of infiltration or unclear results at screening and in order to confirm a CR. Available results of routine samples will be taken up to 49 days prior to enrollment. Bone marrow biopsy is not required if positron emission tomography (PET) scan is negative in marrow and if not otherwise clinically necessary by investigator discretion.

7.3.11 Core or Incisional/Excisional Biopsy for Biomarker Analysis, MRD by NGS, Cell of Origin, and FISH Analysis (optional)

If as part of the standard institutional procedure, and subject signs the optional consent, a tumor affected lymph node or tissue sample for the diagnosis of relapsed/refractory DLBCL will be collected for subjects enrolled into the study. In addition, a second biopsy is to be collected only in subjects who consent to additional biopsies. Samples should be collected 10 weeks after starting blinatumomab. Sites will process all tissue samples as outlined in the laboratory manual. Submission of formalin-fixed paraffin embedded tumor tissue sample blocks are preferred; slides or fresh frozen tissue are acceptable. All tissue sample preparation guidelines and requirements will be outlined in the laboratory manual.

Tissue will be used for exploratory analyses which may include and not be limited to MRD and immunohistochemistry (IHC). In addition, cell of origin analysis may be performed to determine DLBCL subtypes, and FISH analysis may be performed to determine gene rearrangements associated with double/triple hit DLBCL, if this information is not reported in the CRF under Medical History (see Section 7.3.3).

7.3.12 Tumor Response Assessment

7.3.12.1 Assessment of Disease and Tumor Imaging

PET/CT scans with whole body images, from base of skull to mid-thigh, will be conducted. If PET scan at screening is negative for disease involvement in the neck, screening and subsequent CT scans may not include neck. PET/CT should be performed until documented complete remission, PD/**relapse**, or 24 months after the first assessment. **Response assessment will also be conducted at the time of treatment discontinuation due to clinically suspected disease progression or relapse.** Imaging is not required beyond confirmed progression **or relapse** (unless subject meets criteria to continue therapy beyond radiographic progression **or relapse** as outlined in Section 7.3.12.4). For lymphomas that are not fluorodeoxyglucose (FDG)-avid at screening, PET does not need to be repeated in follow-up assessments.

Examinations should be consistent across timepoints and include the following information: amount of tracer, location of injection, arm location, scan delay. The following data should be collected per site: standard procedures, height, weight, gender, administration dose, time between dose administration and imaging, blood glucose level, time between blood glucose level sampling, and tracer injection.

PET images should be converted to standardized uptake value maps to support comparison across timepoints and to standardize viewing conditions; CT and anatomical coverage includes neck, chest, abdomen, and pelvis.

Enhanced MRI will be allowed to replace CT strictly when iodinated contrast is contraindicated.

Criteria for Assessment of Disease

Antitumor activity will be evaluated using the following criteria:

- Recommendations for Initial Evaluation, Staging, and Response Assessment of Hodgkin and Non-Hodgkin Lymphoma: The Lugano Classification (Cheson et al, 2014) ([Appendix I](#))
- Revised Response Criteria for Malignant Lymphoma. (Cheson et al, 2007) ([Appendix J](#))

The Lugano Classification (Cheson et al, 2014) will be applied by the site as the primary measure for subject eligibility, assessment of disease response and as a basis for all protocol guidelines related to disease status and subject management (eg, discontinuation of study therapy). Meanwhile, Cheson 2007 Revised Response Criteria will continue to be used for the assessment of disease response to keep consistency through the study.

7.3.12.2 Initial Disease Assessment

Initial disease assessment or tumor imaging must be performed within 28 days prior to the first dose of trial treatment. The site study team must review pre-trial images to confirm the subject has measurable disease as defined in the inclusion criteria.

Disease assessments or scans performed as part of routine clinical management are acceptable for use as the screening scan if they are of diagnostic quality and performed within 28 days prior to the first dose of trial treatment. Computed tomography and PET should be used throughout the study at time-points designated in Schedule of Assessments (Table 7-1 and Table 7-3). For lymphomas that are not FDG-avid at screening, PET does not need to be repeated in follow-up assessments.

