4.1 Inclusion Criteria

In order to be eligible for participation in this trial, the subject must meet the following criteria:

101. Subject/legally acceptable representative has provided written informed consent prior to initiation of any study-specific procedures.
102. Age \geq 18 years at the time of informed consent
103. Have histologically confirmed DLBCL that is either:
 - Refractory after at least 1 regimen of systemic chemotherapy and/or targeted therapy, and refractory is defined as progressive or stable disease as the best response to the most recent systemic chemotherapy regimen or disease progression or relapse within 12 months after autologous stem cell transplantation; when using PET for assessment, for subjects with refractory disease and who have received radiotherapy, PET positivity should be demonstrated no less than 6 weeks after the last dose of radiotherapy (Crump et al, 2017; Neelapu et al, 2017; Cheson et al, 2007), or
 - In first or later relapse if have received at least 2 systemic regimens since time of diagnosis, or
 - Relapsed post-autologous or allogeneic HSCT with adequate organ function after proximity to transplantation time exclusions as specified in Exclusion Criteria 208 and 209
104. Have measurable disease defined as at least 1 lesion that can be accurately measured in at least 2 dimensions with spiral computed tomography (CT) scan. Minimum measurement must be either $>$ 15 mm in the longest diameter OR $>$ 10 mm in the short axis.
105. Demonstrate adequate organ function as defined in Table 4-1.

Table 4-1. Adequate Organ Function Laboratory Values

System	Laboratory Value
Hematological	
Absolute neutrophil count (ANC)	≥ 1,500/mcL
Platelets	≥ 100,000/mcL
Hemoglobin	≥ 9 g/dL or ≥ 5.6 mmol/L
Renal	
Creatinine OR Measured or calculated ^a creatinine clearance (CrCl) (glomerular filtration rate (GFR) can also be used in place of creatinine or CrCl)	≤ 1.5xULN OR ≥ 60 mL/min for subject with creatinine levels >1.5 x institutional upper limit of normal (ULN)
Hepatic	
Total bilirubin	≤ 1.5xULN OR Direct bilirubin ≤ ULN for subjects with total bilirubin levels > 1.5 x ULN
AST (SGOT) and ALT (SGPT)	≤ 2.5xULN OR ≤ 5xULN for subjects with liver metastases
Coagulation	

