4.2 Exclusion Criteria

Subjects meeting any of the following exclusion criteria will not be eligible to participate in this study:

201. Richter's transformation (DLBCL arising in the setting of prior chronic lymphocytic leukemia) or PMBCL
202. History or presence of clinically relevant CNS pathology such as epilepsy, paresis, aphasia, stroke, severe brain injury, dementia, Parkinson's disease, cerebellar disease, organic brain syndrome, or psychosis.
203. Has disease that is suitable for local therapy administered with curative intent.
204. Currently receiving treatment in another investigational device or drug study, or less than 30 days since ending treatment on another investigational device or drug study(s). Thirty days is calculated from day 1 of protocol-specified therapy
205. Has a diagnosis of immunodeficiency or has received systemic steroid therapy (in excess of 10 mg daily of prednisone equivalent) or any other form of immunosuppressive therapy within 7 days prior to the first dose of protocol specified therapy.
206. Has had a prior anticancer mAb within 30 days prior to first day of study treatment or who has not recovered (ie, \leq grade 1 or at baseline) from adverse events due to such agents administered more than 30 days earlier.
207. Has had prior chemotherapy, targeted therapy, or radiation therapy within 14 days prior to first day of study treatment or who has not recovered (ie, \leq grade 1 or at baseline) from adverse events due to such previously administered agents.

Note: Subjects with \leq grade 2 neuropathy or \leq grade 2 alopecia are an exception to this criterion and may qualify for the study.

208. Has undergone prior allogeneic HSCT:
- within the last 5 years
- OR
- greater than 5 years ago but has active graft versus host disease (GvHD) requiring systemic treatment.
209. Has received autologous HSCT within 6 weeks prior to start of treatment.
211. History of other malignancy within the past 3 years with the exception of:
- Malignancy treated with curative intent and with no known active disease present for ≥ 3 years before enrollment and felt to be at low risk for recurrence by the treating physician
 - Adequately treated non-melanoma skin cancer or lentigo maligna without evidence of disease
 - Adequately treated cervical carcinoma in situ without evidence of disease
 - Adequately treated breast ductal carcinoma in situ without evidence of disease
 - Prostatic intraepithelial neoplasia without evidence of prostate cancer

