6.9 Excluded Treatments, Medical Devices, and/or Procedures During Study Period

Subjects are prohibited from receiving the following therapies during the Screening and Treatment Phase with protocol specified therapy (including retreatment for post-complete remission relapse) of this trial:

- antineoplastic systemic chemotherapy or biological therapy
- immunotherapy not specified in this protocol
- chemotherapy not specified in this protocol
- investigational agents other than blinatumomab and pembrolizumab within 30 days prior to the start of protocol specified therapy
- radiation therapy

Note: Radiation therapy to a symptomatic solitary lesion or to the brain may be considered on an exceptional case by case basis after consultation with the sponsor. The subject must have clear measurable disease outside the radiated field. Administration of palliative radiation therapy will be considered clinical progression for the purposes of determining PFS.

- Live vaccines within 30 days prior to the start of protocol specified therapy and while participating in the trial. Examples of live vaccines include, but are not limited to, the following: measles, mumps, rubella, chicken pox, yellow fever, rabies, BCG (Bacillus Calmette-Guérin), and typhoid (oral) vaccine. Seasonal influenza vaccines for injection are generally killed virus vaccines and are allowed. However, intranasal influenza vaccines (eg, Flu-Mist®) are live attenuated vaccines, and are not allowed.

- Systemic glucocorticoids or other immunosuppressants for any purpose other than those which are protocol mandated or given as treatment for an adverse event.

Note: Inhaled steroids are allowed for management of asthma or chronic obstructive pulmonary disease (COPD).

Subjects who, in the assessment by the investigator, require the use of any of the aforementioned treatments for clinical management should be removed from protocol specified therapy but will continue to be followed on the trial. Subjects may receive other medications that the investigator deems to be medically necessary.

For other medications that are prohibited in this trial, refer to exclusion criteria in Section 4.2.

If a subject starts a new anti-lymphoma treatment within 30 days of their last dose of protocol-assigned therapy, a safety follow-up visit should be conducted immediately prior to starting any new treatment, including HSCT conditioning regimens.

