^h Report AEs occurring after enrollment **through the last safety follow-up visit that occurs 30 days (+7 days) following cessation of treatment. Report SAEs that occur after signing of the informed consent form through 90 days following cessation of treatment, or 30 days following cessation of treatment if the subject initiates new anticancer therapy, whichever is earlier. After this period, report SAEs suspected to be related to IP, and fatal SAEs regardless of causality.**

ⁱ Available results of brain contrast-enhanced MRI performed up to 8 weeks prior to first day of study treatment are acceptable. In case of neurologic AE ≥ grade 3 a brain MRI should be performed.

^j If PET scans and CT scans are done separately, they must be within the ± 3 day window and a maximum of 72 hours apart. If PET and CT are acquired on the same day, it is strongly recommended that PET is performed prior to the CT with IV contrast.

^k Enhanced MRI will be allowed to replace CT strictly when iodinated contrast is contraindicated.

^l After week 10 and during LTFU, subjects should have scans performed per the regular frequency every 12 weeks (± 3 days). PET/CTs should be performed until documented complete remission, progressive disease, or 24 months after the first assessment. Response assessment will also be conducted at the time of treatment discontinuation due to clinically suspected disease progression. In case of suspected pseudo-progression, repeat imaging performed 4 to 8 weeks from initial assessment suspicious for PD. Subjects who receive at least 1 full dose of pembrolizumab who discontinue from all study treatment in cycle 1, for whatever reason, shall undergo a PET/CT scan between 14 to 28 days after last pembrolizumab exposure.

^m Scans done within 28 days prior to first dose may be used in place of protocol-required assessments.

ⁿ If PET scan at Screening is negative for disease involvement in the neck, screening and subsequent CT scans may not include neck. If PET scan at Screening is positive for disease involvement of the neck, subsequent CT scans must include neck.

^o For lymphomas that are not FDG-avid at screening, PET does not need to be repeated in follow-up assessments.

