7.3.12.3 Timing of Disease Assessments

Uniform disease response assessments will occur initially at 10 weeks (D64) (± 3 days) after treatment start of blinatumomab and thereafter every 12 weeks (± 3 days). **The scan on Day 64 will be compared to the scan from screening. Any other scan thereafter will be compared to the scan that was done immediately before it.**

PET/CT should be performed until documented complete remission, PD, **or relapse** or 24 months after the first assessment. Response assessment will also be conducted at the time of treatment discontinuation due to clinically suspected disease progression **or relapse**. If PET scans and CT scans are done separately, they both must be within the ± 3 -day window and a maximum of 72 hours apart. If PET and CT are acquired on the same day, it is strongly recommended that PET is performed prior to the CT with IV contrast. Subjects who receive at least 1 full dose of pembrolizumab who discontinue from all study treatment in cycle 1, for whatever reason, shall undergo a PET/CT scan between 14 to 28 days after last pembrolizumab exposure.

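### A baseline scan up to 28 days old can predate therapy given as late as 15 days before day 1, so a partial response may be credited to the study drugs in error

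*Protocol*

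**What the plan says.** - **Age of the baseline scan.** Protocol 7.3.12.2: "Initial disease assessment or tumor imaging must be performed within 28 days prior to the first dose of trial treatment". Routine-care scans qualify: "Disease assessments or scans performed as part of routine clinical management are acceptable for use as the screening scan". The only conditions are adequate image quality and the same window. Footnote m of Table 7-1 and footnote l of Table 7-3 repeat the rule: "Scans done within 28 days prior to first dose may be used in place of protocol-required assessments".
- **Prior therapy.** Exclusion 207: "Has had prior chemotherapy, targeted therapy, or radiation therapy within 14 days prior to first day of study treatment". Exclusion 205 bars systemic steroids above 10 mg/day prednisone equivalent within 7 days of first dose. Exclusion 206 is longer: "Has had a prior anticancer mAb within 30 days prior to first day of study treatment".
- **Radiotherapy.** For refractory subjects assessed by PET, inclusion 103 adds that "PET positivity should be demonstrated no less than 6 weeks after the last dose of radiotherapy".
- **During screening.** Protocol 6.9: "Subjects are prohibited from receiving the following therapies during the Screening and Treatment Phase". The list includes chemotherapy, radiotherapy and systemic glucocorticoids. Screening begins at consent (section 5) and lasts up to 21 days, with no minimum (section 3.5.1).
- **Response.** Protocol 7.3.12.3: "The scan on Day 64 will be compared to the scan from screening".

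No section requires the baseline scan to come after the last prior therapy, or to be repeated if therapy intervenes. The SAP's baseline definition (section 6.1) falls back on the most recent pre-treatment value and does not require one taken after therapy.

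**The concern.** The scan window is longer than the washout. A site can therefore keep every rule while the subject has a routine scan, then a cycle of chemotherapy, a course of radiotherapy or a burst of steroids, then consents and starts blinatumomab. Day 64 is then compared with a picture of the disease before that therapy, and any shrinkage it caused is counted for the study drugs.

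There is no control arm to absorb this, and response is assessed by the sites. Day 64 is the only scheduled assessment in the first 12 weeks, so the 12-week objective response rate depends largely on this one comparison. A response in that period also places the subject in the SAP's Responder Analysis Set, on which duration of response is summarised. The primary endpoint, incidence of DLTs, is untouched.

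**Working it through.** The plan states no figure on this point, so there is none to reproduce. The check is a day count, in days before first dose.

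**Inputs**
- Oldest acceptable scan: 28 (7.3.12.2 and the footnotes).
- Latest permitted chemotherapy, targeted therapy or radiotherapy: 15, since 207 bars 14 or fewer.
- Latest permitted higher-dose steroids: 8, since 205 bars 7 or fewer.
- Screening length L: any value up to 21. Under 6.9 the therapy must precede consent, so its last day is at least L + 1.

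**Formula.** Longest interval from baseline scan to last prior therapy = 28 − max(w, L + 1), where w is 15 or 8.

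| Screening length | w = 15 | Steroids, w = 8 |
|---|---|---|
| 7 days | 28 − 15 = 13 | 28 − 8 = 20 |
| 14 days | 28 − 15 = 13 | 28 − 15 = 13 |
| 18 days | 28 − 19 = 9 | 28 − 19 = 9 |
| 21 days | 28 − 22 = 6 | 28 − 22 = 6 |

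The interval never reaches zero.

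**What other rules remove**
- Anticancer antibodies: the 30-day rule (206) exceeds 28, so antibody treatment cannot fall after the scan.
- Other investigational drugs: 30 days (204), likewise.
- Autologous transplant: 6 weeks = 42 days (209), likewise.
- Radiotherapy in refractory subjects assessed by PET: 42 days (103), likewise.

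What remains is chemotherapy, non-antibody targeted therapy, steroids, and radiotherapy in relapsed subjects. Refractory subjects had at best stable disease on their most recent chemotherapy (unless they qualified by early failure after autologous transplant), so marked shrinkage from that regimen is unlikely. Relapsed or bridged subjects are the main route.

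**Which responses depend on the baseline scan**
- Partial response does. On CT, Appendices I and J require at least a 50% decrease in the sum of products of diameters; the PET version in Appendix I requires uptake reduced from baseline.
- Complete response does not in the same way. Appendix I requires a PET score of 1 to 3, or target nodes of 1.5 cm or less with no extralymphatic disease; Appendix J requires disappearance of disease. It would be miscredited only if disease had already cleared before day 1.

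**Size of one miscredited response.** 1/6 = 16.7 points; 1/10 = 10.0 points.

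**Persistence needed.** Day 64 is 63 days after day 1. Therapy ending 15 days before day 1 is therefore 63 + 15 = 78 days before the Day 64 scan; for steroids, 63 + 8 = 71 days.

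**The case against.** The strongest reply is that the plan already narrows the gap and that a false response must survive a long time. Antibody regimens are out, radiotherapy is out for refractory subjects assessed by PET, and a full 21-day screening leaves only 6 days. Shrinkage must last about 78 days with no contribution from the study drugs. Protocol Table 2-2 lists PFS of 49 days, 83 days and 1.6 to 2.5 months for several agents, and section 2.1 describes remissions as usually short. Untreated growth between an old scan and day 1 would bias response downward. A subject who would have responded anyway adds no inflation. The endpoints are secondary and descriptive.

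All of this stands and limits the point; none of it closes the gap. Screening has no minimum length, relapsed subjects lack the radiotherapy safeguard, and growth in untreated subjects does not correct the classification of treated ones.

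A reader might go on to infer an expected inflation by applying published response rates to the affected subjects. The documents do not support that. The share of subjects affected appears nowhere. The response rates in Table 2-2 run from 2% to 74% and describe whole regimens, not therapy squeezed into 13 days. The 63% quoted in section 2.1 comes from rituximab-containing salvage, and exclusion 206 keeps rituximab out of the gap.

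**Conclusion.** The overlap is real and follows from the text. Chemotherapy, non-antibody targeted therapy or radiotherapy can end up to 13 days after the baseline scan, and steroids up to 20 days after it if screening lasts 7 days or less. A partial response can then be credited wrongly, at 17 points per subject in a cohort of 6 and 10 points in a cohort of 10. This assumes that sites use the full scan window and treat before consent; how often they do is unknown, so no expected bias can be stated.

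Two further inferences should be resisted. Complete response is not equally exposed, because its criteria are absolute. The requirement of 1 response in 6 or 2 in 10 for entering Part 2 is no longer at risk, because SAP section 11 records that Part 2 will not proceed. The point is a worthwhile and cheap improvement to the reporting of objective response and of the duration-of-response set; it does not bear on the primary result.

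**What to change.** **In the SAP (main change).** Flag every subject with anti-lymphoma therapy or systemic steroids between the baseline scan and day 1, apart from protocol dexamethasone premedication. Use two sources: the prior anti-cancer therapy CRF (named in SAP section 6.1) and the concomitant medication CRF, which covers the 30 days before first dose (Protocol 6.5) and so spans the 28-day scan window. The first alone could miss steroids. List the flagged subjects, and report objective and complete response also with them counted as non-responders in an unchanged denominator. That is a conservative bound, since some of them may truly have responded. The cost is one derived flag and one sensitivity row. It assumes that the forms hold dates good enough to order therapy and scan, and that radiotherapy is recorded on one of them. If no responder is flagged, one sentence in the report settles the matter.

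**In the protocol, for any further enrolment.** Reconcile section 7.3.12.2, footnote m of Table 7-1 and footnote l of Table 7-3 with exclusions 205 and 207, so that the scan used as baseline is one taken after the last prior anti-lymphoma therapy. No washout length needs to change for this. The cost is a repeat scan in subjects treated after their routine scan. After radiotherapy, PET timing needs care, because section 2.1 itself notes post-treatment inflammatory uptake.
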